### ALGORITHM FOR PRIOR, CONCOMITANT, AND POST MEDICATIONS

START DATE	STOP DATE	ACTION
Known	Known	
 
• If medication stop date < study drug first dose date, assign as prior;
 
• If medication start date ≤ study drug first dose date ≤ medication stop date ≤ study drug last dose date, assign as prior and concomitant;
 
• If (medication start date ≤ study drug first dose date) and (study drug last dose date ≤ medication stop date or medication is ongoing), assign as prior, concomitant, and post;
 
• If study drug first dose date ≤ medication start date ≤ medication stop date ≤ study drug last dose date, assign as concomitant;
 
• If (study drug first dose date ≤ medication start date ≤ study drug last dose date) and (study drug last dose date ≤ medication stop date or medication is ongoing), assign as concomitant, and post;
 
• If study drug last dose date < medication start date, assign as post
 

	Partial	Impute stop date as latest possible date (i.e. last day of month if day unknown or 31 st December if day and month are unknown), then: 
 
• If medication stop date < study drug first dose date, assign as prior;
 
• If medication start date ≤ study drug first dose date ≤ medication stop date ≤ study drug last dose date, assign as prior and concomitant;
 
• If (medication start date ≤ study drug first dose date) and (study drug last dose date ≤ medication stop date or medication is ongoing), assign as prior, concomitant, and post;
 
• If study drug first dose date ≤ medication start date ≤ medication stop date ≤ study drug last dose date, assign as concomitant;
 
• If (study drug first dose date ≤ medication start date ≤ study drug last dose date) and (study drug last dose date ≤ medication stop date or medication is ongoing), assign as concomitant, and post;
 
• If study drug last dose date < medication start date, assign as post
 

START DATE	STOP DATE	ACTION
	Missing and medication is not ongoing	
 
• If medication start date < study drug first dose date, assign as prior, concomitant, and post;
 
• If study drug first dose date ≤ medication start date ≤ study drug last dose date, assign as concomitant and post
 
• If study drug last dose date < medication start date, assign as post
 

Partial	Known	
Impute start date as earliest possible date (i.e. first day of month if day unknown or 1st January if day and month are unknown), then:
 
 
• If medication stop date < study drug first dose date, assign as prior;
 
• If medication start date ≤ study drug first dose date ≤ medication stop date ≤ study drug last dose date, assign as prior and concomitant;
 
• If (medication start date ≤ study drug first dose date) and (study drug last dose date ≤ medication stop date or medication is ongoing), assign as prior, concomitant, and post;
 
• If study drug first dose date ≤ medication start date ≤ medication stop date ≤ study drug last dose date, assign as concomitant;
 
• If (study drug first dose date ≤ medication start date ≤ study drug last dose date) and (study drug last dose date ≤ medication stop date or medication is ongoing), assign as concomitant, and post;
 
• If study drug last dose date < medication start date, assign as post
 

	Partial	
Impute start date as earliest possible date (i.e. first day of month if day unknown or 1st January if day and month are unknown) and impute stop date as latest possible date (i.e. last day of month if day unknown or 31st December if day and month are unknown), then:
 
 
• If medication stop date < study drug first dose date, assign as prior;
 
• If medication start date ≤ study drug first dose date ≤ medication stop date ≤ study drug last dose date, assign as prior and concomitant;
 
• If (medication start date ≤ study drug first dose date) and (study drug last dose date ≤ medication stop date or medication is ongoing), assign as prior, concomitant, and post;
 
• If study drug first dose date ≤ medication start date ≤ medication stop date ≤ study drug last dose date, assign as concomitant;
 
• If (study drug first dose date ≤ medication start date ≤ study drug last dose date) and (study drug last dose date ≤ medication stop date or medication is ongoing), assign as concomitant, and post;
 
• If study drug last dose date < medication start date, assign as post
 

START DATE	STOP DATE	ACTION
	Missing and medication is not ongoing	Impute start date as earliest possible date (i.e. first day of month if day unknown or 1 st January if day and month are unknown), then: 
 
• If medication start date < study drug first dose date, assign as prior, concomitant, and post;
 
• If study drug first dose date ≤ medication start date ≤ study drug last dose date, assign as concomitant and post
 
• If study drug last dose date < medication start date, assign as post
 

Missing	Known	
 
• If medication stop date < study drug first dose date, assign as prior
 
• If study drug first dose date ≤ medication stop date ≤ study drug first dose date, assign as prior and concomitant
 
• If study drug last dose date < medication stop date or medication is ongoing, assign as prior, concomitant and post
 

	Partial	Impute stop date as latest possible date (i.e. last day of month if day unknown or 31 st December if day and month are unknown), then: 
 
• If medication stop date < study drug first dose date, assign as prior
 
• If study drug first dose date ≤ medication stop date ≤ study drug first dose date, assign as prior and concomitant
 
• If study drug last dose date < medication stop date or medication is ongoing, assign as prior, concomitant and post
 

	Missing	Assign as prior, concomitant, and post

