**Table 1 Overview of Study Treatment Sequences by Treatment Period**

Treatment Sequence	Period 1	Period 2	Period 3	Period 4
	Week 1	Week 2	Week 3	Week 4
A (n=21)	Placebo	JZP-110 75 mg	JZP-110 150 mg	JZP-110 300 mg
B (n=21)	JZP-110 75 mg	JZP-110 150 mg	JZP-110 300 mg	Placebo
C (n=7)	Placebo	Placebo	Placebo	Placebo

[figure not shown]
During the first 6 days of each treatment period, subjects will take once-daily, oral doses of study drug (75, 150, or 300 mg JZP-110, or placebo) with water at home.

On the last day of each treatment period (i.e., Days 7, 14, 21, and 28), subjects will take their usual PD medications and sleep medications allowed by the protocol as per their usual schedule, and return to the study center where they will take their dose of study drug for that day and undergo assessments for efficacy and safety and tolerability (Visits 3, 4, 5, and 6; see Section 3.5 for the complete schedule of events). Pending the investigator's assessment of safety and tolerability, subjects will proceed to the next treatment period. Subjects will receive their last dose of study drug at Visit 6 (Day 28) prior to the Week 4 visit assessments. Subjects will return for a Safety Follow-up visit (Visit 7) approximately 7 days after the last dose of study drug for follow-up safety assessments. Unless there are outstanding safety issues that require additional follow-up, subjects will be discharged from the study at the Safety Follow-up visit (Visit 7).

The schema of the study is represented in Figure 1.

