### **6.1. STUDY DAY AND PERIOD DAY**

Two different types of study days will be calculated for this study:

1. Study Day will be calculated based on the date of the first dose of study drug and will be used to

show start and stop days of assessments and events during the study. Study Day 1 will be the day of the first dose of study drug.

2. Period Day will be calculated based on the date of the first dose of study drug during the period in which the assessments or events are performed or occur to show start and stop days of assessments or events during the treatment period.

Study Days will be calculated as follows:

- Study Day = (date of assessment or event – date of first dose of study drug) if the date of assessment or event is before the date of first dose of study drug
- Study Day = (date of assessment or event – date of first dose of study drug) + 1 if the date of assessment or event is on or after the date of first dose of study drug

Period Days of each treatment period will be calculated as follows:

- Screening Period Day = (date of assessment or event – date of first dose of study drug during period 1)
- Period Day = (date of assessment or event – date of first dose of study drug during the period) + 1 for periods 1, 2, 3, and 4
- Safety Follow-up Period Day = (date of assessment or event – end date of the last treatment period completed prior to the Safety Follow-up Period) + 1

[figure not shown]

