### 13. PRIOR AND CONCOMITANT MEDICATIONS

Medications will be coded using the World Health Organization (WHO) drug dictionary, version March 2015E and will be classified as follows (see APPENDIX 1 for handling of partial dates for medications.):

- **Prior medications** are defined as any medications that were started prior to the first dose of study drug
- **Concomitant medications** are defined as any medications that were taken on or after the day the first dose of study drug was taken

Prior and concomitant medications will be further classified as follows:

- PD motor functions-related medications are defined as those medications taken for the treatment of PD motor function symptoms.
- Sleep promoting medications are defined as trazodone, benzodiazepines, nonbenzodiazepines (e.g. zolpidem, zaleplon, or eszopiclone), suvorexant, melatonin receptor agonists, GABA receptor agonists opioids, and skeletal muscle relaxants (e.g. baclofen).
- Other medications will be defined as all medications other than PD motor functions and sleep promoting medications.

PD motor functions-related concomitant medications, sleep promoting concomitant medications and other concomitant medications will be summarized separately by anatomical therapeutic class (ATC) level 3 and preferred drug name based on the SAF by treatment group (including all JZP-110 doses pooled into one group) and broken down further by sequence for the placebo treatment group. A medication will be accounted once for each treatment group/sequence during which the medication was taken.

Prior medications will be provided in subject data listings only.

Number and percentage of subjects using a primary therapy device for OSA at Baseline will be summarized based on the SAF by treatment group (including all JZP-110 doses pooled into one group) and broken down further by sequence for the placebo treatment group. For subjects who used a primary therapy device for OSA at Baseline, number and percentage of subjects who have been stable on their primary therapy device settings for at least 4 weeks prior to the Baseline visit as well as if they demonstrated adequate compliance on their OSA device during the same period will be summarized similarly. Number and percentage of subjects who demonstrated adequate compliance with OSA therapy since last visit will be also provided similarly based on the SAF for each post-Baseline visit.

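### If SAP Appendix 1 is programmed as written, a drug with no recorded start date that stopped during treatment gets no category and is left out of the concomitant-medication tables

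*SAP*

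**What the plan says.** SAP Section 13 gives the general definition: concomitant medications "are defined as any medications that were taken on or after the day the first dose of study drug was taken". It refers incomplete dates to Appendix 1. It tabulates concomitant medications only, in three sets (PD motor, sleep-promoting, other); prior medications are listed but not tabulated.

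Appendix 1 then sets out the classification by type of date. For a wholly missing start date with a known or partial stop date there are three rules:

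1. Stop date before the first dose: prior.
2. "If study drug first dose date ≤ medication stop date ≤ study drug first dose date, assign as prior and concomitant".
3. Stop date strictly after the last dose, or drug continuing: the rule ends "medication stop date or medication is ongoing, assign as prior, concomitant and post".

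The same three rules stand in both the known-stop and the partial-stop row. In the partial-stop row the stop date is first imputed to the latest date it could be.

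Where the start date is known or partial, the corresponding rule is "If medication start date ≤ study drug first dose date ≤ medication stop date ≤ study drug last dose date, assign as prior and concomitant".

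**The concern.** A rule of the form X ≤ stop ≤ X holds only when the stop date equals X. Rule 2 is evidently meant to cover every stop during treatment, yet it covers one day. Rules 1 and 3 cover the time before the first dose and the time after the last. The days in between, apart from the first, belong to no rule.

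Appendix 1 is what a programmer would code for records with incomplete dates. A record without a category is not concomitant, so it would not be counted in any of the three tables. Those tables describe the Safety Population by treatment group, in a trial whose primary objective is safety and tolerability.

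**Working it through.** No figure in the plan needs to be reproduced. The check applies each rule to each possible stop day.

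**Inputs**
- First dose = Day 1. SAP Section 6.1: "Study Day 1 will be the day of the first dose of study drug".
- Last dose = Day L. For a completer L is nominally 28. SAP Section 3.1: "Subjects will receive their last dose of study drug at Visit 6 (Day 28) prior to the Week 4 visit assessments". The visit window is ±1 day, so L can be 27 to 29; it is lower for a subject who stops early.
- Missing-start rules 1 to 3 from Appendix 1.
- For comparison, the known-start rules, with a start date before the first dose.

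**Rules in symbols (s = stop day)**
- Rule 1: s < 1
- Rule 2 as written: 1 ≤ s ≤ 1, that is s = 1
- Rule 3: s > L, or ongoing
- Left over: 1 < s ≤ L, that is Days 2 to L, or L − 1 days

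**Result for L = 28**

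| Stop day | Missing start, as written | Missing start, upper bound = last dose | Known start before first dose |
|---|---|---|---|
| before Day 1 | prior | prior | prior |
| 1 | prior, concomitant | prior, concomitant | prior, concomitant |
| 2 | none | prior, concomitant | prior, concomitant |
| 15 | none | prior, concomitant | prior, concomitant |
| 28 | none | prior, concomitant | prior, concomitant, post |
| 29 | prior, concomitant, post | prior, concomitant, post | prior, concomitant, post |

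The gap is Days 2 to 28, which is 28 − 1 = 27 calendar days. Day 28 falls in it because rule 3 is a strict inequality.

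**Other last-dose days**

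| L | Days with no category | Count (L − 1) |
|---|---|---|
| 7 | 2 to 7 | 6 |
| 14 | 2 to 14 | 13 |
| 21 | 2 to 21 | 20 |
| 27 | 2 to 27 | 26 |
| 29 | 2 to 29 | 28 |

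With the upper bound set to L, no stop day is left over for any of these values. The known-start rules were also run for L = 28 over starts from Day −30 to Day 39 and stops up to Day 44; every combination received a category. The gap is therefore specific to the missing-start rows.

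**Records that can fall in the gap.** All three conditions must hold:
- The start date is missing entirely. A record with only a year is partial and follows the sound rows.
- The drug is not ongoing, and its stop date is at least partly known. With both dates missing, Appendix 1 assigns all three categories.
- The stop date, after any imputation to the end of the month or to 31 December, lies after the first dose and no later than the last dose.

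**The case against.** The strongest reply is that this is a copying slip whose intent is plain. The neighbouring rows show the right bound, and the Section 13 definition would call these drugs concomitant. A record with no category at all, not even prior, is likely to be noticed in programming checks, so a programmer may well get it right. That stands, and it is why the loss is stated as conditional on literal programming. It does not remove the error: the SAP contradicts itself, and Section 13 sends exactly these records to Appendix 1.

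A reader might go further and infer that stopped background drugs would disappear from the report, that the background regimen would look more stable than it was, and that the ESS, motor or blood pressure results would be harder to trust. The documents do not support this:
- The tables in Section 13 count drug use by ATC level and drug name. They show neither stops nor changes, so even correctly classified records would not display stability.
- eCRF data are listed with few exceptions (SAP Appendix 2, Listings). Protocol deviations are all listed, and the critical and major ones are summarized with a category for concomitant medications (SAP Section 9). Dose adjustments of PD or sleep medication need sponsor approval and documentation (Protocol Section 5.7).
- The ESS model has no concomitant-medication term (SAP Section 16.1.4). Levodopa equivalent dose and the dopamine-agonist subgroup are defined by use at baseline (SAP Sections 11.1 and 7.5), and per-protocol exclusions by deviations that the sponsor approves (SAP Section 5.4).

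Nor should 27 of 28 days be read as a share of records or subjects. It counts calendar days. Entry requires PD medication that has been stable for 4 weeks before screening, with no change expected (Protocol Section 4.2), which should make stops during treatment uncommon.

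**Conclusion.** The rule is wrong as written in two cells of SAP Appendix 1. Coded literally, it leaves a drug with a wholly missing start date and a stop date after the first dose, up to the subject's own last dose, without any category. The drug is then absent from the descriptive concomitant-medication tables, against the SAP's own definition. The gap is nominally Days 2 to 28 for a completer and Days 2 to L in general.

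The effect stops at those tables. The number of affected records is unknown and may be small or zero, because the documents give no count of missing start dates. The conclusion assumes that Appendix 1 is programmed as it stands.

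**What to change.** In both missing-start rows (known and partial stop date), replace the upper bound so that, after the opening If, the rule reads "study drug first dose date ≤ medication stop date ≤ study drug last dose date, assign as prior and concomitant". Change the matching program line as well. The wording already stands in the other rows of the same table.

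The cost is one word, first to last, in each of two cells, plus the code. It needs no new data and no design decision. One small difference remains: a drug stopped exactly on the last dose date would be prior and concomitant here, while the known-start rows also allow post for that day. It is concomitant either way, so the tables do not change.

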## APPENDIX 2. PROGRAMMING CONVENTIONS FOR OUTPUTS

### OUTPUT CONVENTIONS

Outputs will be presented according to the following:

- **Paper size, orientation, and margins:** The size of paper will be Letter. The page orientation will be landscape; Margins should provide at least 1 inch (2.54 centimeters) of white space all around the page, regardless of the paper size.
- **Fonts:** The font type ‘Courier New’ will be used as a default for tables and listings, with a font size of 8. The font color will be black. No **bolding**, underlining, *italics* or subscripting will be permitted. Super-scripts will be avoided, unless absolutely necessary. Single spacing will be used for all text.
- **SDTM Terminology:** When possible, SDTM controlled terminology (e.g., race) will be used in the tables, listings and figures outputs.

### DATES & TIMES

Depending on data available, dates and times will take the form yyyy-mm-ddThh:mm:ss.

### SPELLING FORMAT

English US, with the exception of the MedDRA SOCs and PTs for which British English will be used.

[figure not shown]
### PRESENTATION OF TREATMENT GROUPS

For outputs where Treatment Sequence will be represented, sequence will be presented as follows and in the order indicated:

Treatment Sequence	For Tables, Figures, and Listings
Sequence A	Placebo/JZP-110 75mg/JZP-110 150mg/ JZP-110 300mg
Sequence B	JZP-110 75mg/JZP-110 150mg/ JZP-110 300mg/Placebo
Sequence C	Placebo/Placebo/Placebo/Placebo

For outputs where treatment groups will be represented, group will be presented as follows and in the order indicated:

Treatment Group	For Tables, Figures, and Listings
JZP-110 75 mg	JZP-110 75 mg
JZP-110 150 mg	JZP-110 150 mg
JZP-110 300 mg	JZP-110 300 mg
JZP-110 pooled	JZP-110 Pooled
Placebo	Placebo

## NUMBER OF DECIMAL PLACES TO BE PRESENTED

For descriptive statistics, the same number of decimal places as in the raw data will be presented when reporting minimum and maximum, 1 more decimal place than in the raw data will be presented when reporting mean and median, and 2 more decimal places than in the raw data will be presented when reporting SD. If the raw data has 3 decimals or more, 3 decimals will be presented for mean, SD, median, minimum, and maximum.

For percentages, 1 decimal place will be presented.

For LS means, LS mean differences, SEs, and CIs, 2 more decimal places than in the raw data will be presented. If the raw data has 3 decimals or more, 3 decimals will be presented.

For p-values, 4 decimal places will be presented.

## LISTINGS

Exception of the AE trigger, prior/concomitant medications trigger, and investigator's signature check box, all data collected on the electronic case report form (eCRF) will be presented in the data listings. The information presented in each listing will be ordered as follows (unless otherwise indicated in the shells): randomized treatment sequence, treatment group, group number (i.e., Group 1, Group 2), subject number, date (where applicable), and time (where applicable).

## APPENDIX 3. LIST OF CLINICAL LABORATORY TESTS

### Hematology

- Complete blood count (CBC), including platelet count and white blood cell (WBC) with differential
- Hemoglobin
- Hematocrit

### Urinalysis

- Appearance
- Bilirubin
- Color
- Glucose
- Ketones
- Leucocyte esterasea
- Nitrite
- Blooda
- pH
- Proteina
- Specific gravity
- Urobilinogen

### Serum Chemistry

- Albumin
- Alkaline phosphatase (ALP)
- Alanine Aminotransferase (ALT)
- Aspartate Aminotransferase (AST)
- Blood urea nitrogen (BUN)
- Calcium
- Carbon dioxide
- Chloride
- Creatinine
- Creatine kinase
- Gamma-glutamyl transferase (GGT)
- Globulin
- Glucose
- Lactate dehydrogenase (LDH)
- Phosphorus
- Potassium
- Sodium
- Total bilirubin
- Direct bilirubin
- Total cholesterol
- Total protein
- Triglycerides
- Uric acid
- TSH (screening only)

a Urine microscopic will be reflexed when blood, leucocyte esterase, or protein are reported greater than trace

